5.4.1 Health economics

Clinical worsening events including need of initiation of targeted PAH treatment, hospitalization due to worsening of right heart function and all cause death or lung-transplantation may be analysed in consideration of health economics in case of sufficient events.

6 Handling of missing values and outliers

6.1 Missing values

All missing data or inconsistencies are to be reported back to the center and clarified by the responsible investigator. Data will be primarily analyzed in the intention-to-treat analysis set. As sensitivity analysis, multiple imputation will be performed and analyzed for the primary endpoint.

6.2 Outliers

Outliers will be defined as values from 1.5 to 3 x interquartile range. Values above 3 x interquartile range will be defined as extreme outliers. For the primary endpoint and secondary efficacy endpoints a sensitivity with exclusion of extreme outliers will be performed.

7 Statistical analyses / methods

Descriptive statistics will be displayed by treatment, including the usual location and scale statistics (mean, median, standard deviation, standard error, first and third quartiles, minimum and maximum) and 95% confidence limits of mean and median.

Frequency tables for qualitative data will be provided.

All variables will be analyzed descriptively with appropriate statistical methods: data (demographic and other baseline characteristics, continuous data at each visit and their change to baseline) will be listed and trial summary tables will be provided.

Demographic variables and baseline characteristics will be summarized by treatment group for the valid for safety / modified intention to treat analysis (ITT). Due to the reduced sample size, centre effects may not be considered in the analyses.

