All secondary analyses will be exploratory and will be considered descriptively. Secondary parameters at baseline and during follow-up will be compared between groups comparing the difference between baseline and follow-up visits. Data will be displayed by means and standard deviations, medians and variances with respective 95% confidence intervals. p-values <0.05 will be considered as statistically significant.

Secondary endpoints will be statistically analyzed by a hierarchical testing strategy using the two-sided student's t-test with comparison of the differences between riociguat (MK-4836) and placebo.

The sequential testing procedure will be performed for these six secondary efficacy variables, strictly in the order listed

- change of cardiac index at rest (baseline to 24 weeks)
- change of total pulmonary resistance (baseline to 24 weeks)
- change of diffusion capacity of the lung (baseline to 24 weeks)
- change of 6-minute walking distance (baseline to 24 weeks)
- change of WHO functional class (baseline to 24 weeks)
- change in QoL (SF-36, physical summation score; baseline to 24 weeks)

It is assumed that WHO functional class will either remain the same, improve by one or two categories, or deteriorate by one category in most cases. A change score (baseline minus end of study) will be calculated, which could go from -3 (class IV at baseline and class I at end of study) to +4 (class I at baseline, death at end of study), but in practice for those patients still alive at the end of the study it will most likely range from -2 to +1.

EudraCT: 2021-001633-40	Version 1.7 15.01.2025	ESRA
-------------------------	---------------------------	------

Exploratory endpoints

Further outcome parameters will be tested exploratory and reported with 95% confidence intervals of the difference between changes in the intervention and placebo group, mean and standard deviation of the mean. Parameters will be analyzed as change from baseline to 24 weeks riociguat (MK-4836) vs. placebo; if available as per visit and assessment schedule, changes between baseline and 12 weeks will also be analyzed.

Patients who withdraw from the study will be asked to complete a final examination which will be included in the data analysis.

Parameters for explorative data analysis include

WHO functional class (baseline to 12 weeks)

Echocardiography

- sPAP, RV-area and RA-area, TAPSE, LV-EI, RV-pump function and LV-EF.

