7.6 Secondary analyses

7.6.1 Efficacy

All secondary analyses will be exploratory and will be considered descriptively. Secondary parameters at baseline and during follow-up will be compared between groups comparing the difference between baseline and follow-up visits. Data will be displayed by means and standard deviations, or in case of non-normally distributed data with medians and variances. Changes will be displayed with means and standard deviations with respective 95% confidence intervals.

Secondary endpoints will be statistically analyzed by a hierarchical testing strategy using the two-sided student's t-test with comparison of the differences between riociguat (MK-4836) and placebo. p-values <0.05 will be considered as statistically significant.

The sequential testing procedure will be performed for these six secondary efficacy variables, strictly in the order listed

- change of cardiac index at rest (baseline to 24 weeks)
- change of total pulmonary resistance (baseline to 24 weeks)
- change of diffusion capacity of the lung (baseline to 24 weeks)
- change of 6-minute walking distance (baseline to 24 weeks)
- change of WHO functional class (baseline to 24 weeks)
- change in QoL (SF-36, physical summation score; baseline to 24 weeks)

Further outcome parameters will be tested exploratory and reported with 95% confidence intervals of the difference between changes in the intervention and placebo group, mean and standard deviation of the mean. Normally distributed data will be compared by two-sided student's t-tests or Welch-test in case of unequal variances. Non-normally distributed data will be analysed by nonparametric analysis methods such as the Wilcoxon-Mann-Whitney test. Frequency data will be compared by Chi square test, if preconditions are met. Parameters will

be analyzed as change from baseline to 24 weeks riociguat (MK-4836) vs. placebo; if available as per visit and assessment schedule, changes between baseline and 12 weeks will also be analyzed.

Patients who withdraw from the study will be asked to complete a final examination which will be included in the data analysis.

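### The 3 x IQR outlier exclusion in the SAP is unsuitable for the ordinal WHO functional class change: if most patients stay in the same class, it can remove every patient who changed

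*SAP*

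**What the plan says.** SAP 6.2 sets two bands. The milder one reads: "Outliers will be defined as values from 1.5 to 3 x interquartile range". The second reads: "Values above 3 x interquartile range will be defined as extreme outliers". Values in the second band are then left out of a sensitivity analysis: "For the primary endpoint and secondary efficacy endpoints a sensitivity with exclusion of extreme outliers will be performed". The section does not say from which quartile the distance is measured, whether low values count, whether the rule applies to visit values or to changes, or whether the IQR is taken over both arms together or within each arm.

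SAP 7.6.1 lists six secondary efficacy endpoints. The fifth is "change of WHO functional class (baseline to 24 weeks)". The planned test is: "Secondary endpoints will be statistically analyzed by a hierarchical testing strategy using the two-sided student's t-test". No test is named for the sensitivity analysis, so I take it to be the same one.

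Protocol 10.3.1 expects functional class to "remain the same, improve by one or two categories, or deteriorate by one category in most cases". Neither document gives the proportion expected to stay the same. The SAP (sections 3 and 8) reports 35 patients in total, and section 11 names SPSS as the software.

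**The concern.** An IQR-based fence presupposes a variable with some spread in its middle half. Functional class change is a whole number, and many patients may score 0. If fewer than about a quarter move in each direction, both quartiles are 0 and the IQR is 0. Three times zero is zero, so every non-zero change lies beyond the fence. The sensitivity analysis would then discard the only patients who carry information on this endpoint and leave a set of identical zeros.

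The open wording adds a lesser problem. An analyst could apply the rule in several ways that give different datasets, after seeing the data. What is at stake is the usefulness of a robustness check, not the main analyses.

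**Working it through.** **Plan's own figure.** The documents give no figure for the outlier rule. The one design figure, 90.2% power with 29 per arm, reproduces (noncentral t, d = 30/34.5: 90.22%) but has no bearing here.

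**Inputs.** n = 35 (SAP 3 and 8). Change values are -1, 0 and +1, with negative meaning improvement, as in SAP Table 2 and the worked example in Protocol 10.3.1. (The formula in that Protocol section, "A change score (baseline minus end of study) will be calculated", gives the opposite sign; two-sided fences do not depend on it.) Quartiles are the SPSS-type weighted average, at positions 0.25(n+1) and 0.75(n+1). The shares improving and worsening are my assumptions.

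**Step 1: when is the IQR 0?** With n = 35 the positions are 0.25 x 36 = 9 and 0.75 x 36 = 27. Q1 is the 9th smallest value and Q3 the 9th largest. Both are 0 exactly when at most 8 patients improve and at most 8 worsen (8/35 = 22.9%).

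**Step 2: what the boxplot rule then does** (exclude below Q1 - 3 x IQR or above Q3 + 3 x IQR).

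| n | Improved | Worse | Q1, Q3 | Fences | Excluded | SD of the rest |
|---|---|---|---|---|---|---|
| 35 | 5 | 3 | 0, 0 | 0, 0 | 8 (all who changed) | 0 |
| 35 | 8 | 8 | 0, 0 | 0, 0 | 16 (all who changed) | 0 |
| 35 | 9 | 2 | -1, 0 | -4, +3 | none | 0.52 |
| 34 | 8 | 2 | -0.25, 0 | -1.0, +0.75 | 2 (both who worsened) | 0.43 |

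In the first two rows the t statistic is undefined. The last row shows a different failure near the threshold. With n = 34 the lower position is 0.25 x 35 = 8.75, so Q1 = -1 + 0.75 x 1 = -0.25. Improvers sit exactly on the lower fence and stay, while both worseners go. The mean change moves from (-8 + 2)/34 = -0.18 to -8/32 = -0.25. One patient without a week-24 assessment is enough to reach n = 34.

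**Step 3: how likely is IQR = 0 at n = 35?** Sum the trinomial probabilities over at most 8 improved and at most 8 worse.

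| Improve | 5% worsen | 10% worsen |
|---|---|---|
| 10% | 99% | 99% |
| 15% | 93% | 92% |
| 20% | 75% | 74% |
| 25% | 47% | 47% |
| 30% | 23% | 23% |
| 40% | 3% | 3% |

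**Step 4: pooled or by arm.** In an arm of 17 or 18, four patients moving one way already make the IQR positive. An arm of 17 with 5 improved loses nobody; an arm of 18 with 2 improved and 1 worse loses all three.

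**Step 5: PVR change.** Use the change figures for the earlier ambrisentan trial in SAP 5.1.1: mean -0.59, SD 0.79 WU (active); mean 0.02, SD 0.76 WU (control). For a normal variable IQR = 1.349 x SD.
- Literal, one-sided reading: the cut-off is 3 x 1.349 x 0.79 = 3.20 WU (active) and 3 x 1.349 x 0.76 = 3.08 WU (control). The chance of exceeding it is 8e-7 (z = (3.20 + 0.59)/0.79 = 4.79) and 3e-5 (z = (3.08 - 0.02)/0.76 = 4.02) per patient.
- Two-sided fences: 0.6745 + 3 x 1.349 = 4.72 SD from the mean, probability 2.3e-6 per patient, or 0.00008 expected exclusions in 35.
- Much heavier tails (t with 3 degrees of freedom): about 0.34 (literal) or 0.45 (two-sided) expected exclusions in 35.

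**The case against.** The strongest reply is that little turns on this. The rule governs sensitivity analyses only. The primary ANCOVA, its Welch fallback, multiple imputation and the main secondary t-tests are untouched. Functional class is fifth in a sequence that SAP 7.6.1 itself calls exploratory and descriptive, and a zero-variance test would be noticed at once. All of this stands and is why the point is minor. It does not make the rule suitable: the one-directional loss at n = 34 still returns a result and would not announce itself.

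Three stronger inferences are tempting.
- *The rule deletes every patient whose class changed.* This holds only when the IQR is 0, and the documents do not give the share unchanged. With 9 of 35 moving one way, nobody is dropped.
- *The rule removes large PVR rises and never falls, so the primary sensitivity analysis is biased.* The literal words allow this, but the 1.5 and 3 x IQR bands match the usual boxplot convention, which is two-sided and measured from the quartiles. Loose drafting is the likelier explanation, and step 5 shows practically no exclusions on either reading under normality. Nor can this be combined with the first inference: loss of every changer needs two-sided fences, whereas the literal rule removes positive scores only.
- *The rule could be applied to raw PVR and remove much of the sample.* On an assumed mean of 2.5 to 3 and SD of 0.4 to 0.8 WU, the literal cut-off would drop about 18% to 99%. SAP 10 did find its outlier among visit 3 values, but SAP 5.1 defines the primary variable as a change, so this is not the natural reading.

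A general dislike of outlier-exclusion checks is a preference, not an error in the plan.

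**Conclusion.** The concern holds for one of the seven endpoints and in conditional form. The rule as written covers functional class change. At n = 35 it removes every changer, and leaves nothing to test, whenever no more than 8 improve and no more than 8 worsen. How likely that is depends on an assumed share of changers and runs from near certainty at 10% improving to about 3% at 40%. The result also rests on SPSS-type quartiles, two-sided boxplot fences and pooling over arms. The missing fences and lower side are a gap in specification with no material effect shown for PVR change. The other five secondary endpoints are continuous or near-continuous, so an IQR of 0 is not expected there. The primary conclusion does not change. Severity: minor.

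**What to change.** In SAP 6.2:
1. Exempt functional class change from the outlier rule. Two-sided fences alone do not cure it, because with an IQR of 0 they still exclude every changer.
2. For PVR, cardiac index, total pulmonary resistance, diffusion capacity, 6-minute walking distance and the SF-36 physical score, define an extreme outlier as a change from baseline below Q1 - 3 x IQR or above Q3 + 3 x IQR, with quartiles pooled over arms.
3. Optionally, for those six endpoints, use a rank-based or robust ANCOVA with the baseline value as the sensitivity analysis, so that every patient is kept. This is a reasonable alternative but is not needed to correct the error.

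Items 1 and 2 cost a few lines of SAP text. Item 3 adds a little programming and a method that readers may know less well.

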7.1 Subject disposition

Type of pulmonary arterial hypertension, hemodynamics, WHO functional class, physical exercise capacity.

7.2 Demography and baseline characteristics

Demographic variables and baseline characteristics will be summarized by treatment group for the valid for safety / modified intention to treat analysis (ITT). Differences will be considered to be at random.

7.3 Prior or concomitant medication and diseases

Frequencies will be listed for each group.

7.4 Exposition to treatment/Compliance

Duration of intake or application, total intake, difference between treatment groups will be analysed and displayed by tabulation of results.

7.5 Primary analysis

Null-Hypothesis (H_0):

The means of the treatment and control group of the primary endpoint is the same at baseline and after 24 weeks.

Alternative hypothesis (H_1):

The mean of the treatment group of the primary endpoint after 24 weeks differs from the mean of the control group.

Type I error

If not mentioned otherwise, all statistical tests will be performed with a type I two-sided error rate of $\alpha = 0.05$

The evaluation of the primary efficacy endpoint will be the change from baseline to 24 weeks in pulmonary vascular resistance. The primary analysis set will be a complete case analysis of the intention-to-treat set.

The main comparison will be the difference in treatment effect between riociguat (MK-4836) and placebo. 95% confidence intervals of treatment difference will also be calculated. The primary comparison will be an ANCOVA model including baseline scores as covariate.

If the preconditions for an ANCOVA analysis are not met, the primary endpoint will be analyzed by robust, two-sided t-test (Welch-test).

A multiple imputation strategy will be implied and analyzed for the primary endpoint (25 imputations) in case of missing data for the primary endpoint.

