1.3 Randomisation, stratification, blinding and replacement of patients

Randomisation was performed by permuted block randomization, stratified by centre. Treatment was allocated by consecutive patient numbers for each centre with respective blinded medication included in the investigational medicinal product packages for each visit.

Patients and investigators were blinded to treatment assignment. The statistician will be blinded to treatment assignment during the statistical analysis. In case of dropout, loss to

follow-up, early withdrawal or other cases of incomplete data, patients were not replaced. However, patients were encouraged to perform their final assessment in case of early termination or withdrawal. The results will be included in the analysis.

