5.1.1 Sample size considerations

In this randomized study patients with early pulmonary vascular disease, indicated by either a) mPAP ≥ 25 mmHg with PVR ≥ 2 to < 3 WU and PAWP ≤ 15 mmHg or b) mPAP $21-25$ mmHg with PVR ≥ 2 WU and PAWP ≤ 15 mmHg were randomized into two groups: one group receiving riociguat (MK-4836) and one placebo group.

In the EDITA study (Pan et al. 2019) SSc patients with mildly elevated mPAP 21-24 mmHg showed a significant reduction of PVR after 6 months of treatment (control-group 0.02 ± 0.76 vs. intervention group -0.59 ± 0.79 WU; effect size 0.77). The changes in PVR were equal to a $23.87 \pm 35.68\%$ reduction in the intervention group and increase by $5.44 \pm 36.61\%$ in the control group (effect size 0.81).

A meta-analysis showed an effect size of 0.88 in both PAH and CTEPH (Zhao et al. 2019).

In the retrospective analysis of patients with CTD-APAH receiving riociguat in PATENT-1 and PATENT-2, mean improvement of PVR after 12 weeks was 132 ± 140 dynes*sec*cm $^{-5}$ in patients with SSc (equals 1.65 ± 1.75 WU; effect size 0.94; Humbert et al. 2017). Patients with SSc-PAH had an effect size of 0.97 (Humbert et al. 2017).

In this study, patients with PVR ≥ 2 WU were to be included. The use of the effect size of the EDITA study for sample size calculation leads most likely to an underestimation of the effect, as in this study with ambrisentan most patients showed a PVR < 2 WU at baseline. Furthermore, all studies reported in the table below had a study duration of 12 weeks. A study duration of 24 weeks will lead to a higher effect and reduction of PVR. Therefore, we assume an effect size of 0.87 of riociguat treatment in this study. A comparable effect size for both included subgroups is anticipated for this study.

Reference	Change / difference in PVR	Effect size	Power	Sample size without dropout
Pan 2019; EDITA	SSc: 0.61 ± 0.79 WU (Ambrisentan)	0.77	80%	56
Pan 2019; EDITA	SSc: $-23.87 \pm 35.68\%$ (n=17) in the intervention group and increase by $5.44 \pm 36.61\%$ (n=15) in the control (Ambrisentan)	0.81	90%	66
Zhao 2019 Meta-analysis Riociguat	PH (PAH and CTEPH): n=695 (Riociguat)	0.88	85%	50
Humbert 2017 CTD-APAH from PATENT-1 and 2	SSc: 1.65 ± 1.75 WU Other CTD: 3.45 ± 3.54 WU (Riociguat)	0.94 0.97	90% 90%	50 48
A sample size of 58 will lead to n=70 with dropout of 15%.				

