With the sample size of 70 patients and a dropout of 15% (valid sample size n = 58), a 90.2% power will be achieved to reject the null hypothesis, if the true treatment effect is at least a 30% reduction of PVR and both groups have an equal standard deviation of 34.5%, according to the two-sample student's t-test, with a type I error of 0.05 (two-sided). A sample of 70 patients (35 patients in each group), allocated in a 1:1 ratio, was therefore aimed to be included.

The primary endpoint will be analyzed by an analysis of covariance (ANCOVA) with baseline values as covariates, which has a power advantage over the student's t-test, achieving a statistical power of 90.2% or more. If the preconditions for ANCOVA are not met, a student's t-test assuming unequal variances (Welch-test) will be performed.

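### The primary analysis should be one unconditional baseline-adjusted ANCOVA; the SAP swaps it for an unadjusted Welch test on a trigger that neither document defines

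*SAP*

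**What the plan says.** SAP 7.5 names ANCOVA with the baseline value as covariate as the primary comparison, followed by the fallback: "If the preconditions for an ANCOVA analysis are not met, the primary endpoint will be analyzed by robust, two-sided t-test (Welch-test". SAP 5.1.1 repeats it: "If the preconditions for ANCOVA are not met, a student's t-test assuming unequal variances (Welch-test) will be performed". The protocol carries the same rule in the synopsis (sample size), in 10.1 and in 10.3.1. None of these places names the preconditions, the checks, the thresholds or the time of checking.

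SAP 5.1.1 justifies ANCOVA as a method "which has a power advantage over the student's t-test". SAP 7.5 adds a sensitivity analysis: "A multiple imputation strategy will be implied and analyzed for the primary endpoint (25 imputations) in case of missing data for the primary endpoint". SAP 1.3 states: "The statistician will be blinded to treatment assignment during the statistical analysis".

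**The concern.** The protocol leaves the detail of the analysis to the SAP, and the SAP leaves the trigger open. Two competent statisticians could follow the text on the same data and report different primary results, one adjusted for baseline and one not.

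The fallback also gives up the baseline adjustment. SAP 8 reports that enrolment ended at 35 of the planned 70, so there is little power to spare. What is at stake is a determinate primary result and, where baseline PVR predicts the week-24 value, precision.

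**Working it through.** **Inputs from the documents.** Effect 0.87 SD (30% difference, SD 34.5%); 29 per group evaluable; two-sided 5% (SAP 5.1.1: "with a type I error of 0.05 (two-sided"); 35 patients in all (SAP 3 and 8).

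**Assumptions, because the documents give no figure.** Split 18/17. Baseline to week-24 correlation ρ = 0.3, 0.5, 0.7, 0.9. Equal SD at both visits. The 0.87 is taken to hold for the change that is analysed, although the plan's inputs are on the percent-change scale.

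**1. The plan's own figure.** Two-sample t-test, 29 per group: noncentrality 0.87/√(2/29) = 3.31 on 56 df, power 90.2%. This reproduces the SAP ("a 90.2% power will be achieved to reject the null hypothesis").

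**2. Unadjusted test at 18/17.** √(1/18 + 1/17) = 0.338; noncentrality 0.87/0.338 = 2.57 on 33 df; power 70.4%. Welch simulates at about 70% for every ρ.

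**3. ANCOVA at 18/17.** The SD of change is σ√(2(1−ρ)) and the residual SD given baseline is σ√(1−ρ²). Their ratio is √((1+ρ)/2), so the noncentrality becomes 2.57/√((1+ρ)/2) on 32 df. Simulation gives slightly less than this formula because it allows for chance baseline imbalance.

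| ρ | √((1+ρ)/2) | ANCOVA, formula | ANCOVA, simulated | HC3 ANCOVA, simulated | Welch |
|---|---|---|---|---|---|
| 0.3 | 0.806 | 87% | 86% | 84% | 70% |
| 0.5 | 0.866 | 82% | 81% | 79% | 70% |
| 0.7 | 0.922 | 77% | 76–77% | 73% | 70% |
| 0.9 | 0.975 | 73% | 71% | 68% | 70% |

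The gap between ordinary ANCOVA and Welch is thus about 16, 11, 6–7 and 1 points. It shrinks if the entry limits compress baseline PVR. With the baseline SD cut to 0.6 of its unrestricted value (assumption), ordinary ANCOVA has 77, 74, 72 and 70%. If the effect is purely proportional to baseline PVR, ANCOVA and Welch are about equal (66–69%).

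**4. Average loss from switching.** This needs a trigger, so two were assumed.

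- *Three 5% checks (equal slopes, Levene, Shapiro-Wilk), normal errors.* The switch fires in 13–14% of trials although all assumptions hold. Power is 83.7, 79.1, 74.8 and 71.1%, against 85.8, 80.6, 75.6 and 71.3% for ordinary ANCOVA: a loss of 2.1, 1.5, 0.8 and 0.2 points.
- *The same checks, skewed or heavy-tailed errors.* The switch fires in 31–94% of trials. With exponential errors at ρ = 0.5 it fires in 94%, and power is 71.8% against 81.2%, a loss of 9.4 points. The largest losses, at ρ = 0.3, are of the order of 12 points; a re-run with exponential errors gave 85.6% against 71.9%. Ordinary ANCOVA keeps type I error at about 4–5.5% in these settings.
- *Levene only, normal errors.* Fires in 3.5–4.0% of trials and costs 0–0.6 points.

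**5. Type I error.** The mechanical three-check switch gives 4.8–5.0% with normal, equal-variance data. Unequal variance matters mainly with unequal arms. At 20 vs 15 or 15 vs 20 with a twofold residual SD ratio, ordinary ANCOVA gives 3.5–7.5% and HC3 4.1–4.6%. At 20 vs 12 with SDs 0.7 and 1.3, ordinary ANCOVA gives 8.7%, HC3 and Welch 4.6%, and the switch 5.9%.

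**The case against.** **The rule is pre-specified, and stating the trigger would be enough.** It stands in the protocol, and 5.1.1 calls the fallback a test for unequal variances, which hints at a variance check that would rarely fire. This stands in part: a written trigger would make the analysis determinate, and with a variance-only trigger the average power loss is negligible. It would still drop the covariate whenever it fired, for no gain that a fixed ANCOVA could not provide.

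**Unequal variance deserves protection.** True in principle. The SAP's table shows an SD that grows with the mean ("SSc: 1.65 ± 1.75 WU Other CTD: 3.45 ± 3.54 WU"), but those are disease subgroups, not arms. The between-arm SDs quoted from the ambrisentan trial are nearly equal (0.76 vs 0.79 WU; 35.68 vs 36.61%). The protection can be kept inside the ANCOVA.

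**Three stronger readings are tempting and are not supported.**

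- A reader might infer inflated type I error or a test chosen by its result. The text authorises no such choice, the rule is carried over from the protocol, the statistician is blinded, and a mechanical switch holds about 5%.
- A reader might infer that Welch leaves unequal slopes or non-linearity uncured. It does not: Welch on the change has no covariate and so makes no slope or linearity assumption. The cost is lost adjustment, not an invalid test.
- A reader might infer that the fallback cannot be combined with 25 imputations, because checks could disagree between imputed datasets. No section says the checks are repeated in each; one sentence carrying over the complete-case choice would settle it.

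**Conclusion.** The point holds as a weakness in the choice of primary analysis. An undefined trigger decides whether the primary result is adjusted for baseline, and firing it costs about 16 points of power at ρ = 0.3, falling to about 1 at ρ = 0.9. These figures rest on the assumed 18/17 split, the assumed correlations and an effect of 0.87 SD on the analysed scale; they shrink or vanish with a narrow baseline range or a purely proportional effect. The average loss cannot be fixed from the documents because it depends on the unstated trigger: from well under 1 point (variance check, normal errors) to the order of 12 points (three checks, strong skew). Validity of the test is not in dispute. Removing the fallback from the primary role is the clear gain; the choice of standard error is a trade-off.

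**What to change.** Before unblinding, in SAP 7.5 and 5.1.1:

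- Make ANCOVA of change in PVR on treatment and baseline PVR the single, unconditional primary analysis.
- Delete the Welch fallback from the primary role and report Welch on the change as a sensitivity analysis.
- Fit the same ANCOVA in each of the 25 imputations and pool.
- Fix the standard error in advance: ordinary with HC3 as sensitivity analysis, or HC3 as primary with a t reference on n − 3 df.
- Record the departure from the protocol synopsis, 10.1 and 10.3.1 in SAP 8.

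The cost is two SAP sentences and one line in section 8, with no new data. HC3 as primary costs about 2–3 power points at 18/17, is slightly conservative (about 3.4–4.3% type I error) and can fall below Welch at ρ about 0.9 (68% against 70%). In return it protects against unequal variances when the arms are unequal. Ordinary standard errors keep those points but carry the type I risk shown above if both arm sizes and variances differ markedly.
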